
Data and if applicable, Specimen Banking:

All psychosocial data, participant tracking and flow, and intervention data will be collected via University of Miami Redcap (https://recap.miami.edu), including previously collected transferred data at Northwester University at Chicago Redcap (https://redcap.nubic.northwestern.edu/redcap/). EMR and physiologic data will also be entered in the Redcap platform. Redcap is securely stored at the Northwestern University (NU) and University of Miami Research Data Centers and available via the web. The data management environment meets the security requirements identified in the Agency Automated Information Systems Security Program (AISSP) Handbook. Redcap requires use of current passwords and log-on codes to protect sensitive AIS (Automated Information System) data from unauthorized access: All system access requires a user name and password. All users who require anything more than "internet user" security to the NU and University of Miami campus network must have a unique ID assigned. The NU and University of Miami ID is used to control access to data files and applications that reside on the network. Every NU and Miami ID is required to have a complex password assigned. Access to Redcap is restricted to participants by means of a username and password incorporated within the participant registration process. Because SQL Server 2008 R2 is integrated with Windows, SQL Server and Windows (MySQL at the University of Miami) authentication is used to prevent unauthorized access. Restriction to Redcap involves maintaining an encrypted list of current users and authorizations based on permissions and roles assigned to each user. NU and the University of Miami provides Redcap administrators with secure Virtual Private Network (VPN) access. Operating system and database based permissions are set by the Redcap administrators. User accounts have limited system resource access. The availability and flow of data is limited to the security access identified and

signed off by management, and is controlled by the database administrator who pre-defines security access levels. This ensures that only data necessary for that individual's work function are viewable. All requests are validated before attempting to submit data to the database. Any internal or stored reference to a participant is accomplished through a unique identifier key. Data is stored and accessed in full compliance with institutional IRB and governmental regulations regarding privacy and security. NU and the University of Miami have a secure data center that houses all servers. This center is limited to authorized employees via the use of a card swiping system and biometric reader on the entrance doors. NU's Department of Medical Social Sciences and the University of Miami IT Department have established standard operating procedures relevant to data retention and removal based on NIH data retention requirements. Sensitive participant identifiers of on-going studies are encrypted and kept confidential. This procedure was initially designed to comply with HIPAA requirements. Terminated studies have all participant identifiers removed from electronic media storage after the retention period. Hard copy documents with participant identifiers will be shredded in a timely manner. NU and the University of Miami provide comprehensive data backup. At NU all data is stored in a dedicated storage server on top of redundant disk array. A snapshot of the virtual machines is taken every night and stored on backup storage that is alternated every two weeks. A full backup of the database is taken every night with incremental backups taken every two hours. Communications lines terminate in locked PBX rooms and in the data center.

Contingency plan for disaster recovery is in place. The NU Research Data Center has two Uninterruptible Power Supplies and a Diesel generator in the event of a power shutdown. These units are tested on a routine basis. At the University of Miami data is encrypted at rest using AES 256 encryption, server is backed up daily. Systems updates are performed monthly and RedCap application upgrades are performed bi-annually. The University of Miami also has an Uninterruptible Power Supplies in the event of a power shutdown.

Miami Site Setting:

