After a participant consents to participate in the study additional health and treatment information will be obtained from their electronic chart. These include: Gleason Score, Prostate Specific Antigen (PSA) results, staging (TNM), time since diagnosis, type of treatments, HIV/AIDS status, Sexually Transmitted Diseases (STD's), Mental Health treatment, Substance Abuse and treatment, Sexual Assault information, Hospitalizations, Cardiovascular conditions, Gastrointestinal conditions, Hepatitis C, Behavioral & Cerebrovascular conditions, Hematology & Oncology, Nephrology and Genitourinary conditions, Respiratory conditions, Rheumatology conditions, other conditions (i.e. Bacteremia, Lupus, Sjorgren's Syndrome). Participants that are enrolled from the community will be asked to sign a medical release form to request this information from their treating physicians. In addition, each participant will be asked to provide a blood sample either in-person via intravenous blood draw (approximately 2 table spoons) or remotely via blood spot collection during each timepoint (T1-T4). Blood samples that are not able to be collected at the scheduled time-point through either of these two methods we will attempt to collect lab data at the next scheduled time-point or not collect them at all. The following are the health information and biospecimens that will be collected and analyzed for exploratory purposes:

Cardiometabolic Health.

For blood samples that are collected in-person via a blood draw procedure we will measure a panel of cardiometabolic risk markers including triglycerides, HDL-cholesterol, blood pressure (SBP/DBP), high sensitivity C-reactive protein (CRP) and fasting glucose following standard procedures used in prior work by the study PI.

154,155 For samples that are collected using a remote Blood Spot procedure we will measure CRP only.

Anthropometric Measurements. For lab samples that are collected in-person at one of our lab locations we will measure height, weight, and waist circumference. These measurements, along with blood pressure, may be used for further data analysis. For samples that are collected remotely we will obtain the height and weight from the participant.

Inflammation.

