C-CBSM will ameliorate the pro-inflammatory phenotype that underlies symptom burden in PC. These effects will be evident at systemic, cellular and functional genomic levels of analysis. For participants who visit our lab location and provide us with an in-person blood sample we will measure IL-1b, TNF- a, IL-6 and IL-10 as markers of systemic inflammation. Among participants who provide us with a blood spot sample we will measure IL-6 and IL-10.

Systemic Level.

For in-person blood collection 8.5-ml of blood are drawn into BD Serum-Separator Tubes and serum harvested via manufacturer's instructions. Aliquots are frozen at -80° C until the study ends. Serum is assayed in a single batch for C-reactive protein (CRP) and interleukin-6 (IL-6)-widely utilized markers of inflammation. Assays are conducted with commercially available Quantikine immunoassays (R&D Systems), with detection thresholds of 0.02 ng/ml (IL-6) and 0.04 pg/ml (CRP). In our work, these kits show intra- and inter- assay CVs< 8%.

Cellular Level.

We activate cells ex vivo with ligands that engage toll-like receptors (TLRs), and monitor production of inflammatory cytokines. This assay stimulates cells with 9 ligands, each optimized to interrogate a specific TLR. ¹⁵⁶ For in-person blood collection 10-ml of blood will be drawn into BD Cell-Separator Tubes. PBMCs are isolated through centrifugation and resuspended in R10 (Sigma). 6 x 10⁵ PBMCs per well are plated with one of the TLR ligands (Invivogen). Plates are incubated for 24 hours under standard conditions, after which supernatants are harvested and frozen at -80°C. Thawed samples are assayed in single batch by electrochemiluminescence in [name] lab on a SECTOR Imager 2400A, using multiplex kits from Meso Scale Discovery. These kits have a 5-log dynamic range, and results are highly accurate and reproducible. In past work, our CVs < 7%. We will measure four cytokines implicated in symptom burden and HRQoL: IL-1b, IL-6, IL-10 and TNF-a and standardized values will be averaged into an unweighted linear composite reflecting the magnitude of inflammatory response, as [name]'s team has successfully implemented in multiple studies. ^{157,158,159} For remote blood spot collection we will not have the capacity to assess cellular production of inflammatory cytokines.

Genomic Level:

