We conduct genome-wide transcriptional profiling of monocytes, the cells that initiate and maintain most inflammatory responses. 160,161 For in-person blood collection 10-ml of blood are drawn into BD Cell-Separator Tubes. After PBMCs have been isolated through centrifugation, they are labeled with immunomagnetic beads against CD14, ¹⁶² a surface marker specific to monocytes. By passing the labeled cell suspensions through Mitenyi's autoMACS instrument, we can acquire a relatively pure (~90%) population of monocytes through positive selection. The acquired cells will then be lysed and stabilized (RNeasy Mini-Kits), 163 and frozen at -80°C until shipment to UCLA for transcriptome profiling assay. Again, both [name] and [name]'s lab have successfully implemented this protocol in previous collaborations with [name]. 157 [name] lab at UCLA will extract total RNA using PCR-clean and RNAse-free techniques, and check sample quantity and quality with NanoDrop 1000 and Agilent Bioanalyzer 2100 instruments. 150ng of the RNA will be transformed to fluorescent cRNA, hybridized to Illumina Human HT-12 bead arrays, and scanned on a Illumina iScan reader. Raw expression values will be quantile-normalized and log-2 transformed for statistical analysis, and the pool of differentially expressed genes will be identified by Linear Mixed Models that compare CBSM and C-CBSM groups, net of demographic and biobehavioral confounders (e.g. age, BMI, co-morbidities and disease-relevant confounders such as time of treatment, time since treatment). Differentially expressed genes are defined as those showing ≥1.5-fold difference between groups and a transcript-level false discovery rate of < 5% (using standard Benjamini & Hochberg stepdown analysis. 164 Up to 10 differentially expressed genes will be re-verified using quantitative RT-PCR with TaqMan gene expression assays (Applied Biosystems Inc.), a one-step enzyme system, 165 and manufacturer's specified thermal cycling protocol on a iCycler real-time PCR instrument (BioRad Inc.). To identify transcription control pathways underlying differential gene expression, we use a 2-sample variant of the Transcription Element Listening System (TELiS). 166 TELiS quantifies the prevalence of transcription factor-binding motifs within promoters of differentially expressed genes. Analyses focus on 3 transcription factors (TFs) by which C-CBSM could affect monocyte inflammatory activity: NF□B, the major pro- inflammatory TF; CREB, a TF that conveys adrenergic signals to monocytes, and whose activity reflects the amount of SNS signal reaching these cells' genome; and glucocorticoid receptor, a TF that propagates cortisol's anti-inflammatory signals within monocytes and, like CREB, indexes how much hormone signal these cells are registering. For the remote blood collection that is collected via dried blood samples (DBS) we will use standard DBS collection procedures that have been well validated and used by our research team (i.e., [name]). 200, 201 Briefly, the samples are collected by pricking the tip of the middle digit with a sterile disposable lancet, and then allowing drops of blood to wick onto filter paper cards Total RNA will be extracted from DBS samples by cutting 2-4 blood spots from the 5-spot filter paper for each sample (using a separate razor blade for each sample to prevent contamination), depositing all filter paper spots from each sample into 370 µL of RLT in an RNAse-free sterile 1.5 ml microcentrifuge tube, incubating the tube for 30 min at 37° C with agitation (1000 rpm), transferring tube contents (including filter paper) into a QIAshredder column for 60 sec microcentrifugation at maximum speed, after which the 360 µL of remaining RLT was processed through the QIAcube nucleic acid extraction system using RNeasy Micro Kit reagents, the manufacturer's standard operating protocol (including DNAse treatment), and a 20 µL elution volume. DBS samples are highly stable, can sit overnight at room temperature and can be mailed for subsequent storage in a -80 freezer. Samples will be stored/batched at [name] lab and mailed to Co-I [name]'s lab at Northwestern

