Blood collection: Participants will also be asked to provide a sample of blood via an intravenous blood draw (approximately 2 table spoons) or a remote home-based blood spot collection. All in- person blood samples will be drawn at one of the Sylvester laboratory locations (Miami, Lennar, Plantation and Kendall) by a licensed phlebotomist. The blood draw will be scheduled by a member of our study team and who will then meet the participant at the preferred lab. A member of our team will take with them appropriate study labels (participant corresponding ID, date, time and timepoint of blood draw). Blood samples will be transported after collection by a member of our study team to [name] laboratory ([name]) and the Department of Pathology, UMHC & Sylvester Cancer Center Lab ([name]) the same day of the blood draw. At the time of the blood draw we will also collect Cardiometabolic and Anthropometric measures (please see Data Collection and Assessment Measure). Remote dried blood spot (DBS) sample collection will be done by using a protein saver card to collect a total of 5 drops of blood. Participants will be mailed a blood spot packet consisting of a set of 2 protein saver cards, lancets, a desiccant, plastic bags, alcohol swabs, and gloves. Participants will also receive hard copy instructions on how to collect and ship samples. Participants will be instructed to collect the blood samples in the afternoon or evening and to send samples to [name] laboratory via FedEx or equivalent for storing. Samples will be stored in a -80 freezer and stored until the end of the study or batched as per PI's discretion and sent to [name] lab for analysis.

Randomization Protocol:

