To Test Exploratory Hypotheses. Aim 3: For Hypotheses 3, the linear mixed model will include fixed effects for the experimental group (C-CBSM vs. CBSM) and observation time (T1-T4), and random effect for person with a compound symmetry covariance structure for the repeated residuals within person. A group by time interaction and post-hoc tests on this model effect will indicate whether and how the time course of the dependent variable differs between the groups. Hypotheses 1-3 will all be analyzed in a similar manner using the outcome measures described in sections C.6.c (Primary Outcomes), C.6.d (Intervention Targets) and C.6.e (Inflammation) respectively. These measures include markers of symptom burden, systemic inflammation, and cytokine production following cellular activation with TLR ligands. Data from gene expression profiling are analyzed using advanced bioinformatics techniques, and described in C.6.e, and as reported previously by Antoni et al.¹²⁴ As each outcome across the different study hypotheses have been carefully selected to address a priori hypotheses, no adjustment for testing of multiple outcomes will be made. However, within the analysis of a specific outcome, Tukey or Bonferroni adjustment will be made for the multiple tests across different time points. The power calculation below adjusts for this multiplicity. Aims 4a-4c: These hypotheses involve tests of proposed mediators of C-CBSM's effect on our primary outcomes. To test mediation with LGM, individual change trajectory (in each outcome of interest) is characterized by an intercept and a slope factor. The overall pattern of change (e.g., linear, quadratic, etc., as informed by analyses for Aims 1-3) for the whole group can be specified by a particular set of coefficients associated with the slope factor. First, we will specify a growth curve model for all participants with an intercept factor representing our outcome of interest at baseline, and the slope factor reflecting the change trajectory in our outcome measure from T1 to T4. For example, to test that increased stress management skills (e.g., MOCS) in the C-CBSM group accounts for reductions in symptom burden (e.g., EPIC-S), we will first test a LGM model without the stress management skills (the mediator) and then test the model with change in stress management skills from T1 to T4. In the model without the stress management skills, we expect that group assignment is not related to baseline symptom burden, but that group assignment will be related to a greater negative change (reduction) in symptom burden scores. In the next step, we will add stress management skills and expect that after adding this mediator in the model, the path between group assignment and symptom burden slope will become non-significant, while the path between the mediator and symptom burden slope is significant thus suggesting mediation. This approach will be applied to test all mediation models in hypotheses 4a-4c. 191,192 Aim 5a-5b: To evaluate moderators and mechanistic pathways of C-CBSM's effects, we will use LMM and latent variable mediation models. For Hypothesis 5a, we will test moderation by including interaction terms between group assignment (C-CBSM vs. CBSM) and each moderator of interest (e.g., SES, acculturation, Hispanic ancestry, treatment type) within the LMM framework. These models will include fixed effects for group, time (T1-T4), the moderator, and the group × moderator and group × time × moderator interactions. A significant three-way interaction (group × time × moderator) will indicate that change in the outcome (e.g., inflammation, symptom burden, HRQoL) over time differs by both treatment group and the level of the moderator. Post-hoc comparisons will clarify the nature of the moderation effects across timepoints. For Hypothesis 5b, we will test whether improvements in cardiometabolic markers (e.g., lipids, fasting glucose, blood pressure) in the C-CBSM group are mediated by reductions in inflammation using SEM. Parallel process LGMs will estimate trajectories for inflammatory markers and cardiometabolic outcomes across time. The indirect effect from group assignment to cardiometabolic outcome slope via inflammation slope will be tested. This approach allows for simultaneous modeling of changes over time, capturing both within- and between-subject effects. Model fit will be evaluated using standard criteria (CFI > .95, RMSEA ≤ .05, SRMR < .08), and significance of indirect effects will be tested using bias-corrected bootstrapped confidence intervals.

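### CRP, IL-6, IL-10 and RNA come from venous blood or dried spots, but no analysis model accounts for sample type

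*Combined protocol and SAP*

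**What the plan says.** All references are to the combined protocol and SAP.

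- **Choice of route.** *Health Information and Biospecimens Collected* lets each man give blood in person "or remotely via blood spot collection during each timepoint (T1-T4"). Nothing fixes the route within a man or balances it between arms.
- **RNA.** *Genomic Level* opens: "We conduct genome-wide transcriptional profiling of monocytes". These are CD14-selected cells of about 90% purity, sent to UCLA. Later in the section: "Total RNA will be extracted from DBS samples", from pieces cut out of the filter paper. No selection step is described for spots, which go to a laboratory at Northwestern.
- **Proteins.** Venous samples give IL-1b, TNF-a, IL-6, IL-10 and CRP. For spots, *Inflammation* says: "Among participants who provide us with a blood spot sample we will measure IL-6 and IL-10"; *Cardiometabolic Health* adds CRP. The stimulated-cell assay, lipids, glucose and blood pressure are in-person only.
- **Model.** Under *To Test Exploratory Hypotheses*, for Hypothesis 3, "the linear mixed model will include fixed effects for the experimental group (C-CBSM vs. CBSM) and observation time (T1-T4"), plus a random person effect and a group-by-time interaction. The gene-level model adds confounders by example: age, BMI, comorbidities and treatment timing.
- **Other covariates.** *Covariates, Cohort Effects, Intent to Treat & Missing Data* admits variables correlated with an outcome at p<.10, with SES and disease factors as examples.

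**The concern.** Four measurements (CRP, IL-6, IL-10 and RNA) are each obtained in two ways, and the choice follows a man's circumstances, not randomisation. If the routes differ in level, a model without a sample-type term reads a shift in route as a shift in biology. Delivery mode for the groups is left to the investigators. If remote sessions go with remote sampling, which is an inference, spot use would move in blocks of 4 to 8 men, and randomisation would not ensure balance.

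For RNA the issue is also one of meaning. *Genomic Level* interprets its results as monocyte inflammatory activity. RNA from unsorted blood cannot carry that reading, however well the arms are balanced.

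At stake are the exploratory analyses that use these markers: Aim 3, Hypotheses 4b and 4c (gene expression as outcome or mediator) and 5b (inflammation as mediator).

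**Working it through.** **The plan's own scale.** *Power Analyses* gives 0.48 SD as detectable for gene expression, with 100 men in the C-CBSM arm at T4, 80% power and two-sided 1%. Taking 100 per arm, (2.576 + 0.842) × √(2/100) = 0.483, so the figure reproduces. It presumes one homogeneous measurement.

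**Assumed inputs.** The documents give neither the spot share nor the level difference between routes. Let D be the spot-minus-venous offset in SD units (0.25 to 1.0), and p the spot share by arm and visit. The range for the between-arm difference in the change of share is 0 to 30 points.

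**Formulas.**
- Shift in the time effect = D × (p at T4 − p at T1).
- Bias in group-by-time at T4 = D × [(change in p, C-CBSM) − (change in p, CBSM)].
- Variance of a man's T4 − T1 change = 2(1 − ρ) + D² × Var(change in route), with marker variance 1. A man who keeps one route has no route change, so his offset cancels.

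**Time effect.** If the share rises from 10% to 50% in both arms and D = 0.5, the shift is 0.5 × 0.40 = 0.20 SD.

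**Group-by-time.** A 20-point difference gives 0.5 × 0.20 = 0.10 SD or 1.0 × 0.20 = 0.20 SD. Set against the plan's 0.48 SD, these are 0.10/0.48 = 21% and 0.20/0.48 = 42%. Over the whole range, bias runs from 0 to 0.30 SD.

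**Simulation.** T4 − T1 change was compared between arms: 100 per arm, ρ = 0.5, route drawn independently at each visit, no true effect, 2,000 runs, nominal two-sided 5%. Monte Carlo error is about √(0.05 × 0.95/2000) = 0.5 points.

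| Spot share T1; T4 C-CBSM / CBSM | D | Bias, no term | Type I error, no term | Type I error, with term |
|---|---|---|---|---|
| 30%; 30 / 30 | 0.5 | −0.004 | 5.2% | 5.5% |
| 10%; 50 / 50 | 0.5 | 0.000 | 5.8% | 5.6% |
| 10%; 50 / 50 | 1.0 | 0.003 | 4.7% | 4.2% |
| 30%; 40 / 30 | 0.5 | 0.050 | 7.0% | 5.4% |
| 30%; 50 / 30 | 0.5 | 0.099 | 10.0% | 5.3% |
| 30%; 50 / 30 | 1.0 | 0.200 | 21.8% | 4.6% |
| 30%; 60 / 30 | 1.0 | 0.302 | 43.1% | 5.7% |

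With the term, bias was within 0.003 SD of zero throughout.

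**Noise with balanced arms.** For 10% rising to 50% with D = 1.0, Var(change in route) = 0.1 × 0.9 + 0.5 × 0.5 = 0.34, so the standard error grows by √1.34 = 1.16. The simulation gives 0.162/0.139 = 1.17. With D = 0.5 it is 0.149/0.143 = 1.04. These depend on many men switching; the documents permit switching but give no frequency.

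**The case against.** The strongest reply is that the plan is silent here, not wrong. The covariate rule could admit sample type. At n = 200, p<.10 needs r of about 1.645/√200 = 0.12. With a 30% share and D = 0.5, p(1 − p)D² = 0.0525 and r = √(0.0525/1.0525) = 0.22, so the variable would enter if screened. That stands. But the rule does not list it, does not say it varies by visit, and would narrowly miss D = 0.25 (r = √(0.0131/1.0131) = 0.11). A known difference in specimen should not depend on a screen, and no covariate makes unsorted RNA into monocyte RNA.

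It also stands that the outcomes concerned are exploratory.

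Five stronger readings are tempting and not supported:

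- **That the arm comparison is confounded.** No section gives spot shares or ties route to arm. With equal shares the simulation shows no bias, even when the share rises over time.
- **That spots are taken later in the day.** The spot instruction is "Participants will be instructed to collect the blood samples in the afternoon or evening". No window is stated for venous draws, so the times are unaligned on paper, not shown to differ.
- **That the two RNA sources are pooled.** The text describes them separately and does not say how, or whether, they are combined.
- **That imbalance alone creates differentially expressed genes.** Dividing log2(1.5) = 0.585 by 0.10 gives 5.85 log2, about a 58-fold route difference. The rule also requires a false discovery rate below 5%. At one visit with 100 per arm and 30% against 40%, a transcript wholly determined by route gives z = 0.10/√(0.35 × 0.65 × 2/100) = 1.48, p about 0.14, which fails. A 20-point gap could pass, but that gap is an assumption.
- **That variance rises 1.2- to 2.0-fold.** The factor 1 + p(1 − p)D² is cross-sectional. The person effect absorbs the offset of a man who keeps one route.

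**Conclusion.** The point holds as a gap in pre-specification with a definite risk. Two specimen types feed the same four measurements, and the stated models have nothing to separate them. The time effect shifts if spot use changes over visits. The group-by-time test, which is the Aim 3 test, is biased only if that change differs by arm: by 0.10 to 0.20 SD, with 10% to 22% type I error at nominal 5%, for a 20-point difference at T4 and an offset of 0.5 to 1.0 SD. With balance, the cost is noise from men who switch. Shares, offsets and ρ = 0.5 are assumptions; bias does not depend on sample size, but the error rates do.

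Markers measured only in venous blood are missing for spot samples, not mixed, and are outside this point. The primary outcomes are unaffected. The change is worth making because it is nearly free and must be fixed before the data are seen to be credible.

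**What to change.** 1. For CRP, IL-6 and IL-10, add sample type at each visit (venous or spot) as a time-varying fixed effect. Do the same where these markers are mediators in the Aim 4 and 5b growth models.
2. Normalise and analyse monocyte and dried-spot transcriptomes as separate data sets. Combine only the arm contrasts, allowing for men who contribute to both, and confine monocyte-specific interpretation to venous RNA.
3. Report the dried-spot share by arm and visit.
4. Do not add the term for venous-only markers or within a single transcriptome data set, where it is constant. Do not add a collection-time term unless spot collection time is recorded: *Blood collection* puts the time on venous labels but mentions none for the mailed kits.

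The cost is SAP wording and a small loss of degrees of freedom. Route must be known to process each sample, so no new data are needed. RNA contrasts lose precision when split by route, and a switcher no longer has a direct change from baseline across routes.
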